### **4.6.1.3 Difference in the key pharmacokinetic parameters $T_{max}$ , $C_{max}$ , and $AUC_{0-60}$ after SC and IV administration of morphine bolus doses in steady state morphine infusion in palliative cancer patients (Outcome f)**

Pharmacokinetic parameters will be assessed by drawing IV blood samples for assessment of morphine serum concentrations from a peripheral venous catheter at 0 (baseline), 2, 5, 7, 10, 12, 15, 20, 25, 30, 40, 50, 60, 75, 90, 105, and 120 minutes after a bolus dose when the patient is assumed to be in a pharmacological steady state\*. (\*>24 hours after start of infusion and >2 hours since last bolus dose).

Detailed sampling procedure is described in *SIM-Study Procedure Manual version 1.3, 07.07.22*. The actual time of pharmacokinetic sampling will be used for the determination of all pharmacokinetic parameters. Concentration values will be considered as missing if they cannot be measured due to analytical or clinical issues.  $AUC_{0-60}$  values will not be determined if fewer than three consecutive concentration values are obtained.

In summary statistics and figures plasma concentrations,  $C_{max}$  and area under the curve (AUC) will, if fitted, be adjusted to a normalized 5 mg morphine bolus dose (actual dose in the study: 2.5–20 mg). Morphine concentration at  $t=0$  during steady state before bolus dose will be standardized.

The main absorption and disposition parameters will be calculated for individual concentration time profiles using, if fitted, a noncompartmental model. An independent samples t-test will be used for comparison of  $C_{max}$  and  $AUC_{0-60}$  between SC and IV groups.  $T_{max}$  will be compared using Wilcoxon rank-sum test.

Linear mixed model with random effects for patients and slopes will be estimated to assess the difference between the groups. The model will include fixed effects for time, dose, age, sex, and weight. Post hoc analyses will be performed to assess between-group differences at each time point as well as within-group changes.

$T_{max}$ : The mean (and median) morphine  $T_{max}$  for each mode of administration will be calculated as the average of the protocol-specified time points at which the plasma morphine is highest in each patient.  $T_{max}$  will be reported in the unit of minutes.

$C_{max}$  : Maximum observed concentration, to be reported in the unit of nmol/l (morphine). The geometric mean for each mode of administration will be calculated.

$AUC_{0-60}$ : Area under the curve from the time of dosing to 60 minutes will be calculated using a log-linear trapezoidal method. The geometric mean for each group will be reported in the unit of nmol/l/hr.

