### **3.5.1 Pharmacokinetic (PK) subgroup analysis set:**

A subgroup of 20 participants that are enrolled in the study and meet eligibility criteria including the serum measurement specific criteria of Hb>9, and consent to blood sampling are considered for PK analyses.

The PK concentration population includes all study participants who have serum samples after bolus dose available for analysis.. The PK analysis population will be defined as all subjects who have PK data from minimum three concentration measurements.

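### The three-concentration thresholds for AUC0-60 and for the PK analysis population are too low: no three consecutive planned samples span more than 20 of the 60 minutes

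*SAP*

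**What the plan says.** SAP 4.6.1.3 (Outcome f) plans samples "at 0 (baseline), 2, 5, 7, 10, 12, 15, 20, 25, 30, 40, 50, 60, 75, 90, 105, and 120 minutes" after a bolus given during steady-state infusion. It defines the parameter as follows: "Area under the curve from the time of dosing to 60 minutes will be calculated using a log-linear trapezoidal method". The stated condition on the amount of data is that AUC0-60 "values will not be determined if fewer than three consecutive concentration values are obtained". On gaps, the section says only this: "Concentration values will be considered as missing if they cannot be measured due to analytical or clinical issues".

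SAP 3.5.1 sets the population: "The PK analysis population will be defined as all subjects who have PK data from minimum three concentration measurements". These need not be consecutive. The subgroup is 20 participants.

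The routes are compared by independent samples t-test for Cmax and AUC0-60 and by Wilcoxon rank-sum test for Tmax. Cmax and AUC0-60 are summarised by geometric means; for AUC0-60, "The geometric mean for each group will be reported in the unit of nmol/l/hr".

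The SAP does not require a pre-bolus sample, a sample at or near 60 minutes, a limit on gaps, or a sample after the observed maximum. It gives no rule for interpolation or extrapolation.

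**The concern.** A trapezoidal area covers only the interval between the first and last sample. Three consecutive values are a small part of this schedule, so a patient whose sampling stops soon after the bolus can pass both stated thresholds without data for most of the window. The analyst must then report a partial area under the name AUC0-60, extrapolate by a method the SAP does not give, or drop the value by a rule made up at analysis.

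Cmax and Tmax are exposed through the population definition. If sampling ends while the concentration is still rising, the highest observed value is simply the last one. A slowly absorbed SC bolus is more open to this than an IV bolus.

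At stake are the three named parameters of the pharmacokinetic study, compared between routes in 20 people. The primary outcome and its decision rule are not affected.

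**Working it through.** **Inputs.** From the SAP: sampling times, window, trapezoidal method and the two thresholds (4.6.1.3, 3.5.1), and 20 participants (3.5.1). Assumed: 10 per route (from 1:1 allocation) and the illustrative curves in step 3. The SAP gives no calculation behind the 20, so there is no plan figure to reproduce. The sample size in section 4.9 is not an input.

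**1. Span of a minimal profile (no kinetic assumption).** Thirteen samples are planned from 0 to 60 minutes, which gives 13 − 2 = 11 runs of three:

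| Runs (min) | Span | Share of 60 min |
|---|---|---|
| 0-5, 2-7, 5-10, 7-12, 10-15 | 5 | 8.3% |
| 12-20 | 8 | 13.3% |
| 15-25, 20-30 | 10 | 16.7% |
| 25-40 | 15 | 25.0% |
| 30-50, 40-60 | 20 | 33.3% |

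No run covers the window.

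**2. Both thresholds together.** Samples at 0, 2 and 5 minutes are three measurements (3.5.1) and three consecutive values (4.6.1.3). Both are met.

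**3. Share of AUC0-60 captured by 0, 2 and 5 minutes (assumed curves).** Linear trapezoid when rising, logarithmic when falling. IV: C(t) = exp(−kt) after a pre-bolus value of 0. SC: C(t) = ka/(ka − k) × [exp(−kt) − exp(−ka·t)].

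Example with elimination half-life 120 min (k = 0.005776) and absorption half-life 10 min:
- IV, 0-2 min: 2 × 0.9885/2 = 0.989. IV, 2-5 min: (0.98852 − 0.97153)/0.005776 = 2.94. Sum 3.93, against 49.7 to 60 min: 7.9%.
- SC, 0-2 min: 2 × 0.129/2 = 0.129. SC, 2-5 min: 3 × (0.129 + 0.288)/2 = 0.626. Sum 0.754, against 39.7 to 60 min: 1.9%.
- SC/IV ratio: 39.7/49.7 = 0.80 on the full window, 0.754/3.93 = 0.19 if both are cut at 5 min.

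Ranges over elimination half-life 60-180 min and absorption half-life 5-20 min:

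| Infusion baseline | IV share | SC share |
|---|---|---|
| None (or subtracted) | 7.5-9.1% | 1.3-3.4% |
| Equal to the bolus increment | 8.0-8.7% | 5.7-6.4% |

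A biexponential IV curve (half-lives 5 and 120 min, 60% fast phase, peak placed at t = 0, no baseline) gives 17%. With a pre-bolus value at t = 0 this falls to about 13%, and with a baseline equal to the increment to about 10%. Across these assumptions the share is about 1-6% for SC and 8-17% for IV.

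**4. Effect of one such profile on an arm of 10.** Let s be the reported share of the true AUC, with otherwise equal values. Geometric mean factor = s^(1/10). Arithmetic mean factor = (9 + s)/10.

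| s | Geometric factor | Fall | Arithmetic factor | Fall |
|---|---|---|---|---|
| 0.02 | 0.676 | 32% | 0.902 | 9.8% |
| 0.05 | 0.741 | 26% | 0.905 | 9.5% |
| 0.10 | 0.794 | 21% | 0.910 | 9.0% |

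**5. Cmax and Tmax.** For an SC curve with half-lives 8 min (absorption) and 120 min (elimination), the peak is at ln(ka/k)/(ka − k) = ln(15)/(0.08664 − 0.00578) ≈ 33 min. A profile stopped before then would report its last sample as the maximum.

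**The case against.** The sentence in 4.6.1.3 is an exclusion: it says when AUC0-60 is not computed. A reader might infer that the SAP declares three values sufficient, but it does not say so. A 5-minute area also fails the SAP's own definition, so a careful analyst would not report it as AUC0-60. This stands as a reading of the words. It does not close the gap: no other condition is stated, the population rule uses the same number, and nothing says what to do with a short profile. The procedure manual is cited for sampling, not for AUC coverage.

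The harm is conditional. It needs a profile that stops early, and the SAP gives no rate. Isolated gaps in so dense a schedule do little damage, and a missing 60-minute sample can be bridged from 50 and 75 minutes. This stands, and the fix allows for it.

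A reader might also infer a known bias against SC, of the order of 17% captured for IV against 2% for SC. The documents do not support that. The contrast needs a heavily weighted fast IV phase, a peak at time zero where the SAP places the pre-bolus sample, and no infusion baseline. With a baseline equal to the bolus increment it shrinks to about 8-10% against 6%. The SAP says the pre-bolus concentration will be standardised without saying how, and the direction of bias depends on which arm loses samples.

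Finally, the 21-32% fall concerns the geometric mean that is reported. The t-test is stated without a log transformation, and on that scale the shift is about 9-10%.

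**Conclusion.** The point holds as a gap in the data-sufficiency rule. The stated thresholds can admit a value that is not AUC0-60, and this follows from the sampling times alone: the best minimal run spans one third of the window and five of the 11 span one twelfth. The consequences rest on assumptions: that some profile stops early, that it is not extrapolated, and that there are about 10 patients per arm. Given those, a single short profile is enough to move an arm's reported geometric mean materially. Neither the size nor the direction of a route bias can be fixed from the SAP. The matter is confined to the PK comparison, but it is worth settling before the concentrations are analysed, because otherwise the choice is made after the profiles have been seen.

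**What to change.** Replace the three-value rule in 4.6.1.3 with a coverage rule:
- Compute AUC0-60 only if a pre-bolus sample exists and there is either a sample at 60 minutes, within a tolerance stated in advance, or samples bracketing 60 minutes (for example 50 and 75) with the interpolation method named.
- Report Cmax and Tmax only if at least one later sample is lower than the maximum.
- Otherwise set that parameter to missing, and report the number set to missing by route.
- Align the PK analysis population in 3.5.1 with these conditions, parameter by parameter.

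If retained concentrations from short profiles are to inform the route comparison through the mixed model, that model needs group and group-by-time terms. The fixed effects now listed for Outcome f are time, dose, age, sex and weight, with no group term.

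The cost is a few lines of SAP text. The downside is that a patient with a broken profile may drop out of one PK parameter in an already small comparison.

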### **2.2 Randomization**

The allocation ratio between treatments is 1:1 with no stratification. The randomization will be performed by using a computer-generated list of blocks of 6-8 patients. The randomization process is described in detail in *SIM-Study Procedure Manual version 1.3, 07.07.22*. Details of the randomization including the final random allocation list are held securely and unavailable to unauthorized trial personnel. Sequentially numbered, opaque, sealed envelopes containing information about patient allocation are located at the Department of Palliative Medicine for emergency and unblinding after 48-hour intervention period.

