#### **2.4.2 Confidence Intervals and p-values**

All calculated p-values will be two-sided. The differences between the groups will be considered significant for p-values less than 0.05. All efficacy estimates will be presented with two-sided 95% confidence intervals. As there is only one primary null hypothesis to be tested in this trial, there will be no adjustments for multiple testing.

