### 4.6.7 Sensitivity Analyses

If larger deviations from the assumptions of linear mixed model will be identified, transformation of outcome variable or model with robust errors, or both, will be considered.

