## 6 Statistical Software

All statistical analyses will be done in Stata v17.0 or later (StataCorp. 2021. *Stata Statistical Software: Release 17*. College Station, TX, USA). For estimation of pharmacokinetic parameters standard software for pharmacokinetic modelling such as the Phoenix WinNonlin software v.8.3 or later or package for noncompartmental analysis in R Statistical Software v4.1.2 or later may be applied as a supplement.

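### The 20-patient PK mixed model has no small-sample inference method specified, and one of its two stated fallbacks, robust errors, is unreliable with 20 clusters

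*SAP*

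**What the plan says.** - **PK set (SAP 3.5.1):** "A subgroup of 20 participants that are enrolled in the study and meet eligibility criteria", with further conditions on haemoglobin and consent to sampling. No split by route is given. Section 2.2 states "The allocation ratio between treatments is 1:1 with no stratification".
- **Tests on the PK parameters (4.6.1.3):** Cmax and AUC0-60 are compared by independent samples t-test and Tmax by Wilcoxon rank-sum test.
- **Mixed model (4.6.1.3):** "Linear mixed model with random effects for patients and slopes will be estimated to assess the difference between the groups". The listed fixed effects are time, dose, age, sex and weight. Neither group nor group-by-time is listed. Each patient has 17 sampling times from 0 to 120 minutes. Between-group differences at each time are to follow as post hoc analyses.
- **Status (4.6.3 and 4.6.4):** the model is listed under primary inferential analysis for outcome f, as an addition to the t-test. Mean differences at each time point are to carry 95% CIs.
- **Fallback (4.6.7):** if larger departures from the mixed-model assumptions are found, "transformation of outcome variable or model with robust errors, or both, will be considered".
- **Error rates (2.4.2):** "All calculated p-values will be two-sided", significance is set at 0.05, and "All efficacy estimates will be presented with two-sided 95% confidence intervals".
- **Software (section 6):** "All statistical analyses will be done in Stata v17.0 or later". No section names ML or REML, a reference distribution or a small-sample correction.

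**The concern.** A mixed model on 20 patients with 17 samples each has 340 rows, but route is constant within a patient. The precision of the route comparison is therefore set by the number of patients less the patient-level parameters, and the extra samples add nothing to that count. With four patient-level covariates the loss is material.

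Whether the reported p-values and intervals have their nominal properties then depends on two choices the SAP leaves open: ML or REML, and a normal or a t-type reference. The robust-error option does not protect against a poor choice, because the sandwich variance is itself biased downwards when there are few clusters and several cluster-level covariates.

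At stake are the only covariate-adjusted PK comparison and the only between-route contrasts over the sampling times. An unstated choice could decide whether these are called significant.

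**Working it through.** **Plan's own figure.** The SAP gives no size or power calculation for the PK set. Its only calculation, for the primary outcome (12 h difference, SD 12 h, two-sided 5%, 90% power), reproduces: t-test power is 89.97% at 22 per arm and 91.2% at the stated 23. It does not bear on this point.

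**Inputs from the SAP.** 20 patients (3.5.1); 17 sampling times, random patient effects and slopes, covariates dose, age, sex and weight (4.6.1.3); two-sided 5% and 95% CIs (2.4.2).

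**Assumptions.** 10 patients per route. A route term is added, because the model cannot estimate the route difference without one. For the simulation, the SDs are 0.5 (intercept), 0.3 per hour (slope) and 0.2 (residual); the SAP gives none.

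**Step 1: degrees of freedom for a between-patient contrast.**
- Adjusted: intercept, route and four covariates are 6 patient-level parameters, so 20 − 6 = 14.
- Unadjusted: intercept and route are 2, so 20 − 2 = 18.

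**Step 2: closed form.** ML divides the between-patient sum of squares by 20 instead of by df, so its standard error is too small by a factor √(df/20). With a normal reference the type I error is P(|t_df| > 1.96·√(df/20)). REML removes that factor, which leaves P(|t_df| > 1.96). The CI width relative to the correct one is 1.96·√(df/20)/t_df,0.975 for ML and 1.96/t_df,0.975 for REML.

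| Contrast | Method, normal reference | Effective critical value | Correct t value | Type I error | CI width ratio |
|---|---|---|---|---|---|
| Adjusted, 14 df | ML | 1.96·√0.70 = 1.640 | 2.145 | 12.3% | 0.76 |
| Adjusted, 14 df | REML | 1.960 | 2.145 | 7.0% | 0.91 |
| Unadjusted, 18 df | ML | 1.96·√0.90 = 1.859 | 2.101 | 7.9% | 0.89 |
| Unadjusted, 18 df | REML | 1.960 | 2.101 | 6.6% | 0.93 |

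**Step 3: simulation under no route effect.** There were 1,500 trials per scenario, with random intercept and slope. Robust errors were clustered by patient with the G/(G−1) factor. Monte Carlo SE is about 0.6 to 0.9 points.

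| Contrast | ML, normal | REML, normal | Robust, normal | REML, t | Robust, t |
|---|---|---|---|---|---|
| Adjusted, route main effect | 14.8% | 9.1% | 15.4% | 7.0% | 12.3% |
| Adjusted, route at 30 min | 13.1% | 8.3% | 13.4% | 5.5% | 11-11.2% |
| Adjusted, route-by-time | 7.9% | 7.0% | 7.3% | 5.2% | 5.9% |
| Unadjusted, route at 30 min | 8.5% | 7.1% | 7.7% | 5.5% | 6.1% |
| Unadjusted, route-by-time | 7.1% | 5.7% | 6.1% | 4.1% | 4.8% |

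The t reference has 14 df for adjusted route contrasts and 18 df otherwise.

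**Step 4: reading.** The excess is largest for adjusted route contrasts under ML or robust errors. For those contrasts a t reference does not rescue robust errors (11-12%), because the variance estimate itself is too small. REML with a t reference brings all five contrasts to about 4-7%.

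**Step 5: other mixed models.** For outcome c with about 46 patients and no covariates, ML with a normal reference gives P(|t44| > 1.96·√(44/46)) = 6.2%, so the problem is essentially confined to PK.

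**The case against.** - **Silence is not a choice.** A reader might infer that the SAP prescribes large-sample inference and that its intervals will therefore be too narrow. The documents do not support that. They name a package, and the analyst may select REML and a small-sample method within it. This objection stands: the defect is an unspecified choice with consequences, and the error rates are conditional on a normal reference.
- **Robust errors are not offered as a small-sample remedy.** Section 4.6.7 names transformation first, makes both options conditional on assumption violations, and says only that they will be considered. This also stands. What remains is that one of the two permitted routes performs poorly at this sample size.
- **The main PK tests are untouched.** Outcome f concerns Tmax, Cmax and AUC0-60, each with one value per patient and a test unaffected by this point. The mixed model is an addition, and its time-point contrasts are labelled post hoc. This limits the reach, but those tests neither adjust for covariates nor compare routes over time, so they do not replace the model.
- **The figures belong to a model the SAP does not list.** The fixed effects contain no group term, and the calculations add one. That is correct, and it is a gap to close in the same edit.
- **The simulated values rest on assumed variance components.** This is true. The closed-form values do not depend on them and point the same way.

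**Conclusion.** The point holds as an unspecified method with a measurable consequence. If a normal reference is used and a route term is included, the adjusted route contrast has a type I error of about 12-15% under ML, about 7-9% under REML and about 13-15% with robust errors, against the stated 5%. In closed form the intervals are 76% (ML) or 91% (REML) of their correct width. For unadjusted or interaction contrasts the error is about 6-9%.

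No single multiple of 5% describes all of these, so it would be wrong to say that false positives are doubled throughout. The conclusions on Cmax, AUC0-60 and Tmax from the t-tests and the rank-sum test are not in question. The primary outcome is not involved.

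The verdict rests on the normal-reference assumption, an even split by route and, for the simulated figures, the assumed variance components. Kenward-Roger itself was not simulated. The evidence for the fix is REML with a t reference on patients less patient-level parameters, which still gave 7.0% for the adjusted main effect.

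**What to change.** - **4.6.1.3 and 4.6.3:** state that the PK mixed model is fitted by REML with Kenward-Roger or Satterthwaite degrees of freedom, and that its fixed effects include group and group-by-time terms alongside those already listed.
- **4.6.7, PK model only:** make transformation, such as log concentration, the fallback and drop uncorrected robust errors. The SAP already reports geometric means for Cmax and AUC0-60, so a log scale fits its own summaries.
- **Optional:** use the same wording for outcome c and the safety mixed models. The gain there is small, since the error is only about 6% for outcome c.

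The cost is a few SAP sentences and a software option. The PK intervals become slightly wider, which is closer to their correct width.

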## 4.6 Methods for Continuous Secondary Outcomes

### 4.6.1.1 *The pain score recorded every 12 hours during the 48 hours period. (Outcome c)*

Linear mixed model with random effects for patients and slopes will be estimated to assess the difference between the groups in overall trend in pain score. The model will include fixed effects for (possibly non-linear polynomial for) time, group dummy and the interaction between the two. Post hoc analyses will be performed to assess between-group differences at each time point as well as within-group changes.

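### PK outcome f: the mixed model lists no route term, the values entering the Cmax and AUC0-60 t-tests are not fixed, and Tmax follows two timing rules

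*SAP*

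**What the plan says.** All three points lie in SAP section 4.6.1.3.

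**Mixed model.** The purpose is stated as "Linear mixed model with random effects for patients and slopes will be estimated to assess the difference between the groups", with post hoc between-group contrasts at each sampling time. The specification is "The model will include fixed effects for time, dose, age, sex, and weight". For pain score (section 4.6.1.1) the corresponding sentence is "The model will include fixed effects for (possibly non-linear polynomial for) time, group dummy and the interaction between the two", and section 4.6.1.2 carries those effects over to bolus counts. Nothing carries them over to outcome f.

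**Scale of the t-tests.** The normalisation sentence opens "In summary statistics and figures plasma concentrations" and says that these, Cmax and AUC will, subject to the undefined condition *if fitted*, "be adjusted to a normalized 5 mg morphine bolus dose". It gives the actual dose range as 2.5–20 mg. The pre-bolus concentration "during steady state before bolus dose will be standardized", with no method given. Cmax and AUC0-60 are then compared by independent samples t-test, without saying on which values. For Cmax, "The geometric mean for each mode of administration will be calculated"; for AUC0-60, "The geometric mean for each group will be reported in the unit of nmol/l/hr". Section 4.6.3 names the t-test as the inferential analysis for outcome f and the mixed model as an addition.

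**Tmax.** The section first says that every PK parameter is determined from the real sampling times. It then defines the mean and median Tmax from the scheduled times.

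**The concern.** Section 1.3.1.3 asks for the IV–SC difference in Tmax, Cmax and AUC0-60. The t-tests and the Wilcoxon test answer it, and the mixed model supports them.

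A model that exists to compare routes but has no route term cannot deliver the contrasts promised from it. The t-test gap matters more, because those tests carry the answer. With an 8-fold dose range and an unspecified input, the analyst could choose after seeing the data between raw and normalised values, arithmetic and log scale, and total and baseline-corrected concentration. In 20 patients these choices can change power several-fold and also change what is estimated. The Tmax conflict leaves two ways of computing the same parameter.

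**Working it through.** **Plan's own figure.** The SAP gives no sample size or power for outcome f. Its only such figure is 23 per arm for the primary outcome (section 4.9: difference 12 h, SD 12 h, 90% power). This reproduces: the exact two-sample t calculation gives 22.02, rounded up to 23, with power 0.912. It does not bear on this point.

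**Mixed model.** The listed effects give six columns: intercept, time, dose, age, sex and weight. There is no route coefficient, so neither an overall route difference nor one at a given time can be estimated. Route and route-by-time are the missing columns.

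**Scale of the t-tests.** *From the SAP:* 20 PK patients (3.5.1), 1:1 allocation (2.2), two-sided 5% (2.4.2), doses 2.5–20 mg, i.e. 20/2.5 = 8-fold. *Assumed, not in the SAP:* 10 per arm; bolus exposure proportional to dose; SC/IV ratio r = 0.5; lognormal variation with CV 50%; doses either spread (2.5, 5, 7.5, 10, 15, 20 mg equally likely) or clustered (5, 7.5, 10 mg); where background is present, an average equal to the exposure from a 5 or 10 mg IV bolus and 10% assay error.

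Without background:
- Log SD = √ln(1 + 0.5²) = 0.472. The log difference is ln 2 = 0.693, so the standardised difference is 0.693/0.472 = 1.47. With 10 per arm the simulated power is 87%.
- Spread doses have mean 10 mg and SD 5.95 mg, a CV of about 0.595. Left in the data, they raise the CV from 50% to √(1.25 × 1.354 − 1) = 83%. Simulated power on raw values falls to 37%.

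With background, total exposure = r·(dose/5)·e + background, where e is the between-patient factor (r = 1 for IV). Multiplying by 5/dose removes dose from the first term. If background is unrelated to dose, the same step doubles it at 2.5 mg and quarters it at 20 mg, so the dose spread is moved rather than removed.

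Power at ratio 0.5, from 20,000 simulated trials per row:

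| Doses, background | Raw | Log-normalised, baseline left in | Log-normalised after t=0 subtraction | Log-normalised with t=0 covariate |
|---|---|---|---|---|
| Spread, none | 37% | 87% | – | – |
| Spread, 5 mg independent | 31% | 34% | 71% | 70% |
| Spread, 10 mg independent | 22% | 17% | 55% | 59% |
| Spread, 5 mg proportional to dose | 18% | 64% | 79% | 77% |
| Spread, 10 mg proportional to dose | 11% | 40% | 68% | 69% |
| Clustered, none | 69% | 87% | – | – |
| Clustered, 5 mg independent | 45% | 47% | 74% | 74% |
| Clustered, 10 mg independent | 25% | 24% | 60% | 63% |
| Clustered, 5 mg proportional | 34% | 55% | 76% | 75% |
| Clustered, 10 mg proportional | 19% | 30% | 62% | 65% |

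The subtraction column falls back to the raw scale when any corrected value is non-positive. Repeat runs agree within about one percentage point. Type I error at ratio 1.0 was 4.2–5.3% throughout, with doses drawn from the same distribution in both arms. At ratio 0.8 without background, power is low on either scale: 7% versus 17% (spread) and 12% versus 17% (clustered).

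**Tmax.** Scheduled samples are 2–3 minutes apart up to 15 minutes, so nominal and real times could rank early peaks differently. The SAP gives no sampling-time deviations, so this is not quantified.

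**The case against.** - *Raw values are not prescribed.* A reader might infer that the t-tests will use un-normalised values, since normalisation is mentioned only for summaries and figures. The text does not say so; it leaves the input open. This objection stands, and the point is made only as an unspecified choice.
- *The large power gap assumes no background.* Outcome f is measured during continuous infusion, so total concentrations contain background. A reader might infer that normalisation alone lifts power from 37% to 87%. It does not: with independent background left in, the gain is 2–3 points at 5 mg-equivalent, and at 10 mg-equivalent there is a loss. This stands and shapes the fix.
- *Subtraction is less fragile than a simple model suggests.* Treating exposure as one noisy reading minus another gives a non-positive value in 14–24% of trials (5 mg independent) and 50–58% (10 mg). Cmax is a maximum over many samples. Under assumed curve shapes it gave about 0.2–1% and 1–6%, and AUC0-60 gave 5–12% and 27–38%. So the high rates must not be applied to Cmax.
- *The missing route term is a drafting slip.* The purpose sentence makes the intent plain, and the model is only additional. Both are true, but the list still has to be completed.
- *Mean differences against geometric means.* Section 4.6.4 promises mean differences, but it covers all continuous secondary outcomes and refers to each time point, so the conflict is weak and is not relied on.
- *Baseline may be defined elsewhere.* The SAP refers sampling detail to a procedure manual that was not available. If the manual defines how the t=0 level is standardised, a citation would settle that part.

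**Conclusion.** The point holds in a limited form. The mixed model as listed contains no route contrast, and the two Tmax timing statements contradict each other; both are matters of reading and need no assumptions. The t-test input for Cmax and AUC0-60 is unspecified. How much that matters depends on dose mix, background, variability and the true ratio, none of which the SAP gives. In the illustrations, log normalisation combined with baseline handling gives 55–79% power, against 11–45% on raw totals with background present; normalisation without baseline handling ranges from a clear gain to a loss. The simulation treats exposure as a single quantity, so it is a simplified stand-in for both Cmax and AUC0-60.

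It would be wrong to infer harm to the trial's main conclusion. The primary outcome, the trial's sample size and type I error are unaffected. The change should be made before the PK data are analysed; the Tmax part is minor.

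**What to change.** 1. Add route and route-by-time to the fixed effects for outcome f, as for pain score. Cost: wording only.
2. State that Cmax and AUC0-60 are compared on baseline-handled, dose-normalised, log-transformed values, reported as geometric mean ratios with 95% CIs, and remove or define the *if fitted* condition. Cost: normalisation assumes exposure proportional to dose. If exposure follows dose^0.7 to dose^1.2, power without background is still 81–87% and type I error about 5%.
3. State how the t=0 level enters, or cite the document that defines it. Either option is workable:
   - Subtract it before scaling to 5 mg. This targets the bolus ratio itself, but needs a stated fallback for non-positive values, which are rare for Cmax and more frequent for AUC0-60.
   - Use the log dose-normalised t=0 value as a covariate, so that the t-test becomes a two-group regression. This never fails on the log scale and has similar power, but it estimates a ratio of total exposure: about 0.69 (5 mg-equivalent) or 0.77 (10 mg-equivalent) when the true bolus ratio is 0.5.
4. Use real sampling times for Tmax, or limit the real-time rule to the other parameters.

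No new data are needed.
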